## 1 SYNOPSIS

Title of the Protocol: Arginine Supplementation in Sickle Cell Anemia: Physiological and Prophylactic Effects
CSCC Protocol Number: April 2, 2007, Version 6.0
Overview: Nitric oxide is an important inflammatory mediator produced from arginine by nitric oxide synthase. Nitric oxide has a multitude of functions which could impact favorably on vaso-occlusion in sickle cell disease. Oral arginine has been shown to raise levels of nitric oxide. This study will test whether daily oral arginine results in an increase in nitric oxide and other beneficial effects in patients with sickle cell disease. The results of this study will serve as the basis for further clinical trials to determine if daily arginine is a beneficial therapy for patients with sickle cell disease.
CSCC Protocol Chair: [name]
Intervention: Patients will be treated with one dose of oral arginine (0.05 g/kg/day) or placebo for 12 weeks.
IND Holder: [name]
IND Number: 59,995
Objectives: Primary Objective(s): To assess the physiological effects (both beneficial and deleterious) of the administration of oral arginine in patients with SCD. Secondary Objective(s): To evaluate the effect of daily oral arginine on clinical vaso-occlusive events in SCD patients.
Hypotheses/Estimates: The hypothesis of this study is that oral arginine, given daily, will increase nitric oxide production which will, in turn, produce beneficial effects on vascular homeostasis in sickle cell disease.
Criteria for Evaluation: Efficacy: Primary Endpoint: Efficacy will be determined by changes in three laboratory parameters which will serve as surrogates for potential clinical benefit: nitric oxide, Gardos channel activity, and RBC density. Secondary Endpoint: sVCAM, Nitrotyrosine, 8-iso-PGF2a, Ektacytometry, endothelin-1, fetal hemoglobin (Hb F) and echocardiogram results as well as clinical outcomes including hospitalizations, ER visits, and pain medication use. Safety: SAFETY VARIABLES TO BE COLLECTED IN ADDITION TO ADVERSE EVENTS
Study Design: Double-blinded, placebo-controlled, phase II trial in which 94 patients will be randomized to receive one dose of arginine or placebo for 12 weeks.
Study Population: Male or female Hb SS patients age 5 or more years Major Inclusion Criteria: History of at least one pain event in last 12 months Major Exclusion Criteria: Major organ dysfunction, treatment with hydroxyurea or transfusion within 3 months, history of recent priapism or retinopathy, pregnancy.
Sample Size: 94 (grouped into 48 children and 46 adults)
Randomization: One dose of arginine hydrochloride will be evaluated in this trial. Patients in each age group (children and adult) will be treated with one dose of arginine (0.05 g/kg/day) or placebo divided for BID dosing. Sixteen patients will be randomized to each dose level and placebo. Randomization will be stratified by center to preserve balance across treatment groups.
Data Analyses: Within each age group, we will evaluate differences in laboratory measures among the 3 groups (1 arginine group, one placebo group, and the previously collected arginine dose group) using random effects analysis of covariance techniques. Here the change in laboratory measures over each measurement time will act as the dependent variable of interest and the treatment status as the grouping factor. The baseline value of the laboratory measure and the time of the measurement visit will act as the fixed effect covariates and each patient

**Title of the Protocol:** Arginine Supplementation in Sickle Cell Anemia: Physiological and Prophylactic Effects  
will have a random intercept. Additionally, each laboratory measurement will be summarized by age group (pediatric and adult), treatment arm, and measurement time. No interim analyses are planned for this study. The SDCC will be responsible for data management and analysis.

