### 7.2 Description of Type of Study

The general research design of this proposal is a double blinded, placebo-controlled, Phase II trial of oral arginine in SCD patients. Due to concern over differences in response due to age, two age groups will be tested independently—children under 18 and adults 18 and over. Patients in each age group (children and adult) will be treated with one dose of arginine (0.05 g/kg/day) or placebo divided for BID dosing. Sixteen patients will be randomized to the arginine and placebo arms. Added to this will be the 16 children and 14 adults previously randomized to the high dose arginine arm (0.10 g/kg/day). In total, 94 patients (48 children and 46 adults) will be evaluated as to the effects of arginine.

**Figure 7.1.** Study Design

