## 9.2 Randomization and Masking

Randomization will be stratified by center and age group to preserve a balance across treatment groups. No other stratification factors will be used and a block randomization method will be used to ensure balance within the center-age strata. A randomization list for each center and age group will be generated by the SDMC and kept at the SDMC. The pharmacist dispensing study drug at the site will have access to this list. Additionally, emergency unblinding envelopes will be generated and sent to the sites. These will be labeled with the subject's ID on the outside and can be opened to reveal the randomized dose in case of an emergency. After the completion of the trial, all sealed randomization envelopes will be returned to the SDMC for confirmation of maintenance of the mask.

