## 12 STATISTICAL ANALYSIS

### 12.1 Sample Size

A total of 94 patients will be enrolled into this trial over an 18-month period (48 children and 46 adults). It is estimated that 6 to 8 clinical centers (12-16 patients per center) will be required to enroll sufficient patients in this period.

Initially, subjects were randomized to one of three treatment groups: placebo, low dose arginine and high dose arginine. With this amendment, subjects are now only randomized to placebo and low dose arginine. Subjects will be stratified by age group (5-17 years,  $\geq 18$  years) and since there could be drastic differences between these groups, they will be analyzed separately. Thus, all sample size calculations will be for each of these two groups.

We have identified three measurements that are of primary interest: Nitric Oxide, Gardos Channel Activity, and erythrocyte density (MCHC  $>41$ ). We will measure our panel of investigative laboratory measures at various time points between baseline and sixteen weeks (up to eight timepoints). In order to avoid making more assumptions than necessary for our sample size calculations, we will use a simpler model that reflects a single timepoint. Specifically, we will use a one-way ANOVA with three groups (one for each treatment arm) modelling the change from baseline in each of our three measurements. We will additionally assume a two-sided alpha of 0.05. The hypothesis tested from this model will be any difference in mean change from baseline between the three treatment groups.

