The literature suggests that the average NOx level in stable sickle cell patients is 25.5, with a standard deviation of 2.2. We assume that both groups start out with this mean and that the placebo group maintains this level across the length of the study. Based on preliminary findings, we expect a minimum increase of 1.75 for the high dose in the mean change from baseline NOx and the low dose to have a related 1.375 increase. If we assume that the variance is equivalent for the pre and post measurements, we can calculate the variance of the difference as the sum of the pre and post variances minus twice the covariance between pre and post measurements. Thus, our variance estimate depends greatly on the correlation between the pre and post measurements. Assuming a range of correlations (0.3, 0.5, and 0.7), we can then estimate the sample size we will need to detect the differences of 1.375 and 1.75 at 80% and 90% power. (See table below.)

Total sample sizes (for each age group) by power and correlation for NOx assuming a 1:1:1 randomization.

		Power	
		80%	90%
Correlation	0.7	27	33
	0.5	42	54

	0.3	57	72
--	-----	----	----

Given that the goal of this trial is exploratory, not confirmatory, we do not need to achieve a significant value on any specific hypothesis test. Additionally, a much larger treatment effect is anticipated, potentially giving us more power. Thus, a reasonable sample size to achieve our goals and provide us with a reasonable estimate, with the potential to see a significant effect is in the range of 48 total subjects in each age group. With the elimination of one dose of Arginine, the sample size of 16 adults per remaining treatment group will be used.

Insufficient data is available in the literature at this time to sufficiently estimate the expected within subject variability (at steady state of SCD) for the Gardos Channel Activity and erythrocyte density (MCHC >41) as measured by Advia. Sample size calculations would therefore be based on unfounded assumptions and are therefore not provided.

Since the rate of dropout cannot be estimated at this time, completion of the study will be monitored and dropouts will be replaced as they occur. This should pose no problem due to the relatively short duration of the trial. All available data on dropouts will be used in the analyses.

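### High-dose allocation closed at this amendment while placebo and low dose continue, and the stated three-group model has no term for randomization period, so high-dose and dose-response contrasts are partly non-concurrent

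*Protocol*

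**What the plan says.** Protocol section 12.1 describes the change in allocation. At the start, "Initially, subjects were randomized to one of three treatment groups: placebo, low dose arginine and high dose arginine". Then: "With this amendment, subjects are now only randomized to placebo and low dose arginine".

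Section 7.2 sets the arm sizes. "Sixteen patients will be randomized to the arginine and placebo arms" in each age group, and "Added to this will be the 16 children and 14 adults previously randomized to the high dose arginine arm". It gives the total as "In total, 94 patients (48 children and 46 adults) will be evaluated as to the effects of arginine". Section 12.1 confirms the adult figure: "With the elimination of one dose of Arginine, the sample size of 16 adults per remaining treatment group will be used".

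The Synopsis (Data Analyses) then fixes one model, within each age group, "among the 3 groups (1 arginine group, one placebo group, and the previously collected arginine dose group"). The dependent variable is change in the measure. The fixed covariates are the baseline value and the time of the measurement visit, with a random intercept per patient. Section 12.4.2 lists treatment and baseline as fixed effects and names non-linear dose relationships as something the model can explore. Section 12.4.4 allows a dose-response analysis if the data support one.

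On randomization, section 9.2 says that "a block randomization method will be used to ensure balance within the center-age strata". The block size and the numbers per arm when high dose closed are not given. Sections 8.3 and 12.1 say that dropouts are replaced, and section 12.1 keeps their data in the analysis.

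**The concern.** Placebo and low-dose patients enrolled after the amendment had no chance of being allocated to high dose. In a single three-group model they nevertheless serve as comparators for it. Visit time does not help, because it is study week within a patient and not calendar date. Any difference between the two periods in how patients' values change over follow-up, whether from site mix, patient mix or assay behaviour, therefore enters the high-dose contrast in proportion to the non-concurrent share of the comparator arm.

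Replacement of dropouts can add to this. A replacement enrolled after the amendment can only go to placebo or low dose, whichever arm the dropout came from.

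The high-dose comparison has a use. Section 5.7.6 expects the trial to inform dosing, and section 12.4.2 says the results will justify and size a phase III trial. A reader comparing the two doses needs to know which contrast is protected by randomization throughout.

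**Working it through.** **Step 1: the protocol's total.** Children: 16 placebo + 16 low dose + 16 high dose = 48. Adults: 16 + 16 + 14 = 46. Total 48 + 46 = 94, as stated. The sum works only if the 16 in each remaining arm include the patients already randomized before the amendment. So some placebo and low-dose patients are concurrent with high dose.

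**Step 2: non-concurrent share f of the placebo arm.** The protocol does not give f. If blocks kept the arms balanced up to closure, high dose at 14 adults implies about 14 placebo adults, so f = (16 − 14)/16 = 0.125. In children high dose had already reached 16, so f is about 0. Balance at closure is an assumption. Simulating permuted blocks of 3, 6 or 9 (assumed) over the protocol's 6 to 8 centers gave on average 13.4 to 13.5 concurrent adult placebo patients, with a 5th percentile as low as 8 in the least favourable setting. For children the average was 15.3 to 15.5, with a lower limit of 10 to 13.

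**Step 3: bias and type I error for adult high dose versus placebo.** Let drift be the difference between periods in mean change from baseline, in SDs of the change score. Its size is assumed. Then:

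- bias = f × drift
- noncentrality = f × drift / √(1/14 + 1/16) = f × drift / 0.366
- two-sided 0.05, 28 degrees of freedom, critical value 2.048

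Section 12.1 gives an NOx SD of 2.2. At its middle correlation of 0.5, the SD of change is 2.2 × √(2 × (1 − 0.5)) = 2.2, which converts the bias to NOx units.

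| Concurrent placebo adults | f | Drift (SD) | Bias in NOx | Noncentrality | Type I error |
|---|---|---|---|---|---|
| 14 of 16 | 0.125 | 0.5 | 0.14 | 0.17 | 5.3% |
| 14 of 16 | 0.125 | 1 | 0.28 | 0.34 | 6.3% |
| 10 of 16 | 0.375 | 1 | 0.83 | 1.02 | 16.8% |

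This single-timepoint two-sample calculation stands in for the longitudinal model, as section 12.1 itself does for sample size.

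**Step 4: cost of using concurrent patients only.** For the protocol's high-dose difference of 1.75 in adults, with SD of change 2.2 × √(2 × (1 − correlation)):

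| Correlation | SD of change | Power, 14 v 16 | Power, 14 v 14 |
|---|---|---|---|
| 0.7 | 1.70 | 77% | 74% |
| 0.5 | 2.20 | 56% | 53% |
| 0.3 | 2.60 | 43% | 40% |

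The loss is about 3 points throughout. In children, with 16 concurrent placebo patients, almost nothing is lost.

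**The case against.** A reader might infer that high dose is in effect a historical cohort and that its comparison with placebo is a before/after comparison. With no concurrent placebo adults (f = 1), the same formula gives a type I error of about 75% at 1 SD drift. The documents do not support this: section 12.1 says the three arms were randomized together at first, and the total of 94 requires pre-amendment patients in the remaining arms.

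Nor does every drift pass through in full. The outcome is change from baseline, adjusted for baseline. A stable shift in level between periods affects a patient's baseline and follow-up alike, and enters only as f × (1 − correlation) × shift. With correlation 0.5, f = 0.125 and a shift of 1 SD of the raw measurement, type I error is about 5.4%. Kit-lot changes concern only secondary endpoints (sVCAM, nitrotyrosine, 8-iso-PGF2α, ET-1); the primary assays have frequent calibration or controls (section 10.1.2). What remains is a period difference in the change itself, such as a different mix of patients or assay drift within follow-up.

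The trial is declared exploratory, dose-response analysis is optional, and the test of any difference among the three groups belongs to the simplified sample-size model in section 12.1. All of this limits the consequence. Section 12.3.1 allows other covariates and section 12.3.2 an examination of center effects, but neither commits to a period term. Section 12.3.3 waives multiplicity adjustment, which does not deal with bias. A covariate list could be left to the statistical analysis plan; here, however, the protocol states the model and places the closed arm in it, so the point concerns stated text.

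**Conclusion.** The point holds in a limited form. The stated model mixes concurrent and non-concurrent comparators in every contrast that involves high dose. Low dose versus placebo is randomized throughout and is not affected.

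The probable size is small. With balanced arms at closure, it is close to nil in children, and in adults type I error is about 6% at a drift of 1 SD in the change score. It reaches about 17% if only 10 of the 16 adult placebo patients were concurrent. These figures rest on an assumed drift and an assumed state of balance at closure, neither of which the protocol gives; replacements enrolled after the amendment could raise the non-concurrent share. The evidence supports a cheap improvement, not a finding that the high-dose results are uninterpretable.

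**What to change.** - Report the numbers randomized before and after this amendment by arm and age group, with replacements identified.
- For high-dose and dose-response contrasts, either add a fixed effect for randomization period (before/after this amendment) to the model in the Synopsis and section 12.4.2, or use only concurrently randomized placebo and low-dose patients. The period term assumes the same shift in every arm.
- State that low dose versus placebo, using all patients in those arms, is the contrast that is randomized throughout.

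The cost is one model term or one restriction, a count table and a sentence. Intervals for the adult high-dose contrast become slightly wider: under the concurrent-only version with balanced arms, about 3 points of power.

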### 9.5.9 Visit Nine

At Visit 9 (Week 14, Study Day  $98 \pm 3$ ), the first follow-up visit, the patient will no longer be on the study drug. The blood drawn for the central lab will not include the Free Radical Tests and the Endothelial Function as in Visits 1, 3, 4, 6, 7, and 8. The blood drawn for the local labs will be enough for the CBC and Reticulocytes tests. Female patients of childbearing potential will receive a pregnancy test. Hospitalization, pain, concomitant medication, and AE information will be collected. For all patients presenting with chest pain or cardiac events, an EKG will be done and CPK isoenzymes and troponin levels will be measured. The discontinuation criteria will be checked to confirm the patient is still eligible for the study.

### 9.5.10 Visit 10

At Visit 10 (Week 16, Study Day  $112 \pm 3$ ), the second follow-up visit, the patient will be seen for the last time. The blood will be drawn and distributed for the central labs in the

same manner that it was collected for Visit 1, 3, 4, 6, 7, 8, and 9. A urinalysis will be performed at this visit. Hospitalization, pain, concomitant medication, and AE information will be collected. For all patients presenting with chest pain or cardiac events, an EKG will be done and CPK isoenzymes and troponin levels will be measured. The discontinuation criteria will be checked to confirm the patient remained eligible throughout the study.

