### *12.4.2 Efficacy*

The goal of this study is to obtain laboratory and clinical information to justify a phase III clinical trial and to provide data to generate accurate power calculations for a subsequent phase III clinical trial. The two age groups (children and adults) will be analyzed separately to assess for differences in response to arginine therapy.

The laboratory variables NO, Gardos Channel activity, sickle red cell density (% of cells >41, as measured by Advia) are of primary interest. Additionally, sVCAM, H3 Technicon, Nitrotyrosine, 8-iso-PGF2 $\alpha$ , Ektacytometry, ET-1, and ECHO will be measured and analyzed as secondary efficacy variables. Since the goal of this protocol is to gain insight into the effect of arginine on multiple physiologic measures (e.g. erythrocyte characterization, endothelial function and free radical biology), we will model the change from baseline for all of the collected measurements over time using random effects longitudinal mixed models, with treatment and baseline measurement as fixed effects. This class of model allows us to control for the correlation induced by having multiple measurements on an individual. We will focus on estimating the relationship between each of the laboratory measures and treatment group over time.

Additionally, by judiciously choosing the structure of the fixed effects over time, we can investigate non-linear dose relationships as well.

Each laboratory measurement will be summarized by age group (pediatric and adult), treatment arm, and measurement time.

Clinical efficacy is a secondary endpoint for this trial. Clinical efficacy data will be collected on all patients. Specifically, patients will be asked for information on emergency room visits and hospitalizations, clinic visits for pain, and pain medication use. All clinical efficacy measurements will be summarized by age group, treatment arm, and measurement time (where applicable). Treatment differences may be examined using appropriate methods as the data permits.

All efficacy data will be analyzed descriptively to provide information for future trials. All analyses will be performed on the intent-to-treat population. Model assumptions will be confirmed and if broken, appropriate methods will be investigated.

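### The synopsis model has no treatment-by-visit term and keeps the off-drug visits at Weeks 14 and 16, so its treatment coefficient mixes on-drug and washout differences

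*Protocol*

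**What the plan says.** The Data Analyses entry of the synopsis states the model. On the outcome and the comparison: "the change in laboratory measures over each measurement time will act as the dependent variable of interest and the treatment status as the grouping factor". On the covariates: "The baseline value of the laboratory measure and the time of the measurement visit will act as the fixed effect covariates". Each patient "will have a random intercept". No interaction of treatment with time is named.

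Section 12.4.2 describes the same analysis differently: "we will model the change from baseline for all of the collected measurements over time using random effects longitudinal mixed models". The only fixed effects it lists are treatment and the baseline value. Visit time is not among them. The section then says: "We will focus on estimating the relationship between each of the laboratory measures and treatment group over time". It adds that the form of the fixed effects over time will be chosen, and gives non-linear dose relationships as the use of that freedom.

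Section 12.1 places the laboratory panel "between baseline and sixteen weeks (up to eight timepoints". Section 7.2.1 limits treatment to 12 weeks. Section 9.5.9 describes Week 14 as "the first follow-up visit, the patient will no longer be on the study drug", and section 9.5.10 makes Week 16 the second follow-up visit. The protocol nowhere removes Weeks 14 and 16 from the treatment comparison or names a primary time point.

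**The concern.** A model with a single treatment term assumes the same arm difference at every visit. That is implausible across the end of dosing: an effect that depends on taking the drug should fade once it stops. If washout visits enter the same coefficient, the result describes neither the effect on treatment nor the effect after it, and it is pulled towards zero whenever the effect fades.

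This touches all three primary endpoints in both age groups. Section 12.4.2 says the study is meant to justify a phase III trial and to support accurate power calculations for it. An effect estimate that is too small for a structural reason works against that purpose. Calling the trial exploratory does not remove the problem, because the issue is what is being estimated and not whether a test reaches significance.

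**Working it through.** **Visit count.** The tables in sections 7.2.2 and 7.2.3 schedule NOx, Gardos channel and Advia at study entry and at Weeks 1, 2, 4, 8, 12, 14 and 16. That is 1 + 7 = 8, which matches the eight time points in section 12.1. So the protocol's own count includes the two off-drug visits. Post-baseline there are 5 on-drug and 2 off-drug visits, an off-drug share of 2/7 = 28.6%.

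**What the coefficient estimates.** With complete, balanced data, a random-intercept model without a treatment-by-time term estimates the plain mean of the visit-specific arm differences. This holds whether time enters as a line or as categories, because both arms share the same visits. Let d be a constant on-drug effect and f the share of it left at Weeks 14 and 16:

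- estimate = d × (5 + 2f)/7
- loss = (2/7) × (1 − f)

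With the low-dose NOx effect of 1.375 from section 12.1:

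| Share left off drug (f) | Estimate | Loss |
|---|---|---|
| 0 | 0.98 | 28.6% |
| 0.25 | 1.08 | 21.4% |
| 0.5 | 1.18 | 14.3% |
| 0.75 | 1.28 | 7.1% |
| 1 | 1.375 | 0% |

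Simulated fits of the synopsis model (800 per arm, true effect 1.75, random-intercept and residual SD both 1.5) lost 26%, 8% and 0% at f = 0, 0.5 and 1. The simulation standard error is about √(1.5² + 1.5²/7) × √(2/800) / 1.75 = 4.6 percentage points, so these agree with 29%, 14% and 0%.

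**Secondary measures.** From the same tables, the off-drug shares are:

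- ektacytometry 2/7 = 29%
- Hb F 1/4 = 25%
- ET-1 and sVCAM-1 1/5 = 20%
- nitrotyrosine and 8-iso-PGF2α 1/6 = 17%

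**If the effect builds slowly.** Suppose it rises in proportion to time up to Week 12. The mean over the on-drug visits is then (1 + 2 + 4 + 8 + 12)/(5 × 12) = 27/60 = 45% of the Week 12 effect. With nothing left off drug, the seven-visit mean is (27/12)/7 = 32%. The choice of on-drug contrast therefore matters as well.

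**A linear interaction is not enough.** Fitting a straight line in time to arm differences of 1 at Weeks 1 to 12 and 0 at Weeks 14 and 16 gives intercept 1.229 and slope −0.0632 per week. The fitted Week 12 effect is 1.229 − 12 × 0.0632 = 0.47 of the true one.

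**Power, illustration only.** Assumptions added here: two arms of 16, SD 2.2, equal correlation ρ between all visits including baseline, baseline-adjusted mean of m visits with variance 2.2² × [(1 + (m − 1)ρ)/m − ρ²], 29 degrees of freedom, two-sided 0.05, and an on-drug effect of 1.375.

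| ρ | On-drug visits (m = 5) | All visits (m = 7), f = 0 | All visits, f = 0.5 |
|---|---|---|---|
| 0.3 | 82% | 59% | 75% |
| 0.5 | 82% | 58% | 73% |
| 0.7 | 91% | 68% | 83% |

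These are not comparable with the table in section 12.1, which rests on a three-group ANOVA at one time point.

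**The case against.** The strongest reply is that the protocol never says the treatment effect is averaged over all visits. A reader might infer that a pooled, diluted effect is the declared target. The documents do not support that. Section 12.4.2, the fuller statement, aims at treatment group over time and leaves the time structure to be chosen, which is compatible with an interaction. Its reference to all collected measurements may mean all assays and not all visits, since section 12.1 uses the same noun for analytes. The eight time points describe when samples are drawn, not which of them enter a contrast. The details could also be settled in a statistical analysis plan. This stands to the extent that the averaging follows from the synopsis model taken literally and is not a stated estimand.

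Second, the sizes need assumptions that the protocol does not supply: full effect from Week 1 and a known decline after Week 12. Table 9.1 asks for a 90-day arginine washout before dosing, so carryover at two to four weeks is not ruled out. The mouse Gardos result in section 5.7.1 followed 10 weeks of diet, so immediate onset is not established either. This also stands, and it makes 29% the loss under one specific pattern and not a forecast.

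Third, the trial is descriptive and every laboratory measure will be summarized by arm and visit, so the pattern would be visible. That lowers the severity. It does not correct the model estimate. Nor does the open time structure in 12.4.2 separate washout: the use it names is dose relationships.

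**Conclusion.** The point holds for the model in the synopsis. Followed literally, that model puts 2 off-drug visits out of 7 into the treatment coefficient for each primary measure, and section 12.4.2 does not put this right.

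For an effect that is constant on drug, and with complete data, the loss runs from 29% (nothing persists) through 14% (half persists) to none (all persists). The off-drug share, and so the possible loss, is smaller for every secondary laboratory assay except ektacytometry. If the effect builds slowly, the shortfall against Week 12 can exceed 29%, but part of that comes from the early visits and not from washout. The power figures rest on further assumptions and only illustrate the direction.

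It would go too far to conclude that the primary estimates will be biased by 29%, or that the trial is badly underpowered for this reason: the persistence of effect is unknown and the protocol does not require a significant result. This is a should-fix, because the trial is exploratory and per-visit summaries are already planned.

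**What to change.** Bring the synopsis and section 12.4.2 into line with one model: change from baseline on baseline, treatment, visit as a categorical factor and treatment-by-visit, keeping the random patient intercept. Name the primary contrast in advance as an on-drug one: the arm difference averaged over Weeks 1 to 12, or at Week 12 if the effect is expected to build slowly. Report Weeks 14 and 16 as a separate washout contrast. Do not use a treatment-by-linear-time term in place of the categorical interaction.

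The cost is wording and a few degrees of freedom for the interaction, a modest price even with 16 per arm. If the effect did persist fully off drug, leaving those two visits out of the primary contrast would also give up a little precision. No visit, sample or patient is added.
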